7 RISK/BENEFIT ASSESSMENT

7.1 Risk Category/Potential Risk

Minimal risks to study participants are expected. For the assessment interviews, the primary risk is invasion of privacy, breach of confidentiality (if safety issues such as elder abuse are detected), or mild reactions of distress or fatigue. Given that assessments are conducted in the participant's homes, others could be present, which risks revealing the participant's involvement in the study. Participants will have full discretion in having others present. Assessment measures and procedures have been safely used in previous research with older adults; no sustained negative effects from assessments are expected, but negative outcomes cannot be ruled out.

Similarly, with regard to the intervention sessions, some participants may experience some discomfort, or fatigue in having study staff in their homes for the intervention sessions. Additionally, as the intervention sessions may include exercises to enhance function and reduce the risk of falls, some patients may be physically fatigued at the end of these sessions (in particular, the OT sessions can include physical activities such as simplifying tasks and the environment, using assistive devices, and balance and fall recovery techniques to decrease fear of falling). The original *CAPABLE* was well received and tolerated by older adult participants, however, who uniformly reported that the intervention benefited them.^{81, 82} Additionally, as *CAPABLE Transitions* likewise aims to improve home safety by reducing the presence of environmental hazards (home hazards is an intermediate outcome), we expect that those participating in our intervention will be at less risk of experiencing adverse events such as falls.

If a participant's cognition declines such that she is unable to work towards her study goals, our interventionists will work with the participant to identify new goals to work on. If the capability of a participant changes (for worse or better) such that there are no further identified feasible goals to work on, we will end the intervention. Our intervention is multifaceted (e.g., handyworker, OT, and RN), meaning that only those components for which there are no clear objectives or workable goals may terminate. This also could occur if a participant achieves their goals quickly, thereby only requiring a few of the interventionist sessions rather than all of the possible sessions.

We will train both the study interviewers and interventionists to handle these minimal discomforts if they occur (e.g., if a participant is becoming fatigued, can change activities or terminate the session) and will conduct assessments regarding intervention safety at every in-home visit. During these assessments, study staff will regularly query for the occurrence of adverse events. Although we do not anticipate there to be any serious adverse events related to our intervention, staff will systematically monitor for these events during the intervention and follow-up periods and report them should they occur (consistent with RSRB policy 801, "Reporting Research Events").

7.2 Methods and Timing for Assessing, Recording, and Analyzing Safety Parameters

At each intervention session, study staff will inquire about the occurrence of adverse events and significant adverse events since the last visit (timing of intervention sessions shown in Table 2). This schedule of assessments is such that, as the intensity of the intervention is the greatest, so will we monitor for the occurrence of adverse events most intensely, which will help us identify the presence of any study-related adverse events.

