6 STUDY PROCEDURES

6.1 Schedule of Evaluations

| Study Activities | Initial Screening (Day-28 to Day-1) All Participants | Baseline Enrollment, Assessment, and Randomization Visit (Day 0) All Participants | Intervention Arm: OT and RN Visits (< 11 total visits within 5 months) AND CHHA CAU Services* (variable intensity and timeframe) | Comparator Arm: ONLY CHHA CAU Services* (variable intensity and timeframe) | 2 nd Assessment Visit (Day 90) All Participants | Final Assessment Visit (Day 180) All Participants |
|--|--|---|---|---|--|---|
| Inclusion/Exclusion Criteria | X | X | X | X | | |
| Informed Consent (Written) | | X | X | X | | |
| Determination of Capacity for Informed Consent | | X | X | X | X | X |
| Enrollment/Randomization | | X | X | X | | |
| Study Intervention | | | | | | |
| Study OT Visits (<6 Visits, Occur at 1-4 Week Intervals) | | | X | | | |
| Study RN Visits (<5 Visits, Occur at 1-4 Week Intervals) | | | X | | | |
| Study Handyworker Visits (<2 Visits, Occur at ~2 Week Intervals) | | | X | | | |
| Study Assessments | | | | | | |
| Sociodemographics | | X | X | | X | |
| Health and Functioning | | X | | | X | X |
| Mental Health and Cognitive Functioning | | X | | | X | X |
| Home Environment | | X | | | X | X |
| Medical and Non-Medical Services Use (Self-Reported) | | X | | | X | X |
| Study Partner Questions (If Applicable) | | X | | | X | X |

| | | | | | | |
|--|--|---|---|--|---|---|
| Chart Extraction (e.g., Conditions, Medications, Medical Services Use, Communications) | | X | | | X | X |
| Study Fidelity Measures (e.g., Participant Engagement) | | | X | | X | X |
| Intervention Feedback | | | | | X | X |
| Adverse Events | | X | X | | X | X |
| | | | | | | |

*Both treatment groups receive CHHA CAU services (intervention arm receives *CAPABLE Transitions* and CHHA CAU; comparator arm only receives CHHA CAU). CHHA CAU services can include nursing, home health aide, medical social work, and occupational, physical, and speech therapy services. CHHA clinicians will determine the types and duration of services that CHHA clients in this group receive, which will be completely independent of the research study. The duration of CHHA can vary dramatically across CHHA clients (e.g., range from a single visit to having weekly visits for more than a year).

Table 3. Operationalization of the primary and secondary outcomes and study covariates.

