| Variable | Variable Type | Assessment Schedule | Data Source |
|--|---------------------------|--------------------------|---|
| Primary Outcomes | | | |
| • Participants Screened, Enrolled, and Retained | Continuous, Proportion | Monthly | Study Documentation |
| • Intervention Fidelity: Adherence, Dose, Quality | Continuous, Proportion | Varies | Audio Recording, Study Documentation, Self-Report |
| • Intervention Perceived Benefit (based on Szanton et al., 2019 ⁴⁰) | Likert Items, Open-Ended | 3, 6 Months | Self-Report, Proxy-Report |
| • Data Completeness for Clinical Outcomes | Proportion | 6 Months | Study Documentation |
| Secondary Outcomes (Primary Clinical Outcomes) | | | |
| • Home Time | Continuous | 3, 6 Months | Chart Extraction, Self-Report |
| • Quality of Life (EQ-5D-5L, ICECAP-O ^{66, 67}) | Variety of Variable Types | Baseline, 3 and 6 months | Self-Report |
| • Service Utilization: ED, Hospital, Nursing Home Use | Continuous | Baseline, 3 and 6 months | Chart Extraction, Self-Report |
| Sociodemographics | | | |
| • Contact Information | Address, Phone Number | Baseline, 3 and 6 Months | Self-Report |
| • Age, Date of Birth | Continuous, Date | Baseline | Self-Report |
| • Race, Ethnicity, Sex | Categorical | Baseline | Self-Report |
| • Formal Education, Marital Status, Living Arrangement, Income, Home Ownership and Type | Categorical | Baseline | Self-Report |
| • Caregiver or Receive Caregiving | Categorical | Baseline, 3 and 6 Months | Self-Report |
| • Children and Siblings | Continuous | Baseline | Self-Report |
| • Health Insurance | Categorical | Baseline | Self-Report |
| Health and Functioning | | | |
| • Social Needs Questionnaire ²³ | Continuous | Baseline, 3 and 6 Months | Self-Report |
| • Self-Rated Health Status (Adapted from JHU) | Likert Items | Baseline, 3 and 6 Months | Self-Report |
| • Main Medical Problem, Concerns, and Goals | Open-Ended | Baseline, 6 Months | Self-Report |
| • Medication Adherence Measure (DOSE-Non-Adherence) ⁶⁸⁻⁷¹ | Continuous | Baseline, 3 and 6 Months | Self-Report |
| • ADL (Adapted from JHU) | Continuous | Baseline, 3 and 6 Months | Self-Report |
| • IADL (Adapted from JHU) | Continuous | Baseline, 3 and 6 Months | Self-Report |
| • PROMIS* – Isolation v2.0, Mobility v2.0, Pain Interference v1.1, Ability to Participate v2.0 ⁷² | Continuous | Baseline, 3 and 6 Months | Self-Report |

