| • Self-Reported Falls (based on CDC's Behavioral Risk Factor Surveillance System) ⁷³ | Variety of Variable Types | Baseline, 3 and 6 months | Self-Report |
| • Intervention Perceived Benefit (based on Szanton et al., 2019 ⁴⁰) | Likert Items, Open-Ended | 3, 6 Months | Self-Report |
| • COVID-19 Effect Scale (modified from Impact of Event Scale-6 ⁷⁷) | Likert Items, Open-Ended | Baseline, 3 and 6 Months | Self-Report |
| Mental Health and Cognitive Functioning | | | |

| | | | |
|--|---|---|--|
| 
 • MMSE^{44, 45,86} • PROMIS* – Anxiety v1.0, Depression v1.0, Social Isolation v2.0, Medication Management Self-Efficacy v1.0 | Continuous Continuous | Baseline Baseline, 3 and 6 Months | Self-Report Self-Report |
| Home Environment | | | |
| 
 • Aging Gracefully Home Safety Checklist • Falling Efficacy (FES-I)⁷⁴ | Variety of Variable Types Continuous | Baseline, 3 and 6 Months Baseline, 3 and 6 Months | Interviewer Scored Self-Report |
| Medical and Non-Medical Services Use (Self-Reported) | | | |
| 
 • Non-Medical Human Services Use⁷⁵ • Outpatient Medical Appointments | Continuous Variety of Variable Types | Baseline, 3 and 6 Months Baseline, 3 and 6 Months | Self-Report Self-Report |
| Study Partner Questions | | | |
| 
 • Contact Information, age, sex, race/ethnicity, relationship with participant • Caregiver Support (Adapted from NHATS NSOC Study)⁷⁶ • Quality of Life (EQ-5D-5L, ICECAP-O^{66, 67}) • Main Medical Problem, Concerns, and Goals • ADL^{40, 77, 78} Modified for Proxy Report • IADL^{40, 79} Modified for Proxy Report • Self-Reported Falls (based on CDC's Behavioral Risk Factor Surveillance System)⁷³ • Intervention Perceived Benefit (based on Szanton et al., 2019⁴⁰) • Modified Caregiver Strain Index⁸⁴ • Caregiver Confidence in Medical Sign/Symptom Management⁸⁵ | Variety of Variable Types Categorical, Continuous Variety of Variable Types Open-Ended Continuous Continuous Variety of Variable Types Likert Items, Open-Ended Categorical Likert Items | Baseline, 3 and 6 Months Baseline, 3 and 6 Months Baseline, 3 and 6 months Baseline, 6 Months Baseline, 3 and 6 Months Baseline, 3 and 6 Months Baseline, 3 and 6 months 3, 6 Months Baseline, 3 and 6 Months Baseline, 3 and 6 Months | Proxy-Report Proxy-Report Proxy-Report Proxy-Report Proxy-Report Proxy-Report Proxy-Report Proxy-Report Proxy-Report |
| Chart Extraction | | | |

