6.2.3 Intervention Visits (≤ 11 total visits)

The intervention will proceed as outlined in the *CAPABLE Transitions'* protocol. In addition to delivering the intervention, the study OT and RN will assess the engagement of the study participant or dyad with the intervention. The study OT and RN also will monitor for the presence of study-related adverse events at each visit.

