6.2.4 Follow-Up and Final Assessment Visit

Including the baseline assessment visit (on day 0), study staff will conduct the follow-up and final assessment visits at approximately 90 days (+/- 15 days) and 180 days (+/- 30 days), respectively. Of note, many participants likely still will be receiving the intervention at the 90 day assessment. At the 180 day assessment, however, no participants will be receiving the intervention. These assessment visits will examine the same domains that the baseline assessment examines, but also will include questions to obtain information on intervention feedback. The follow-up assessments will examine the following domains:

- Sociodemographics
- Health and Functioning
- Mental Health and Cognitive Functioning
- Home Environment
- Medical Services Use (Self-Reported)
- Study Partner Questions (If Applicable)
- Chart Extraction regardless of PCP affiliation (e.g., Medical Conditions, Medications, and Medical Services Use, Communication)
- Study Fidelity
- Intervention Feedback (intervention arm only)

The CRC or research assistant also will perform the determination of capacity for informed consent at these 3- and 6-month intervals to screen for whether participants who initially demonstrated capacity for informed consent may have lost the ability to provide informed consent. If they are unable to demonstrate capacity for informed consent, we will go through the entire consent process again, and those unable to demonstrate informed consent only will be able to continue with study participation if they have a legally authorized representative (LAR; see Section 7.3.1 for definition of LAR) who also will need to demonstrate capacity to provide informed consent prior to signing the informed consent document. If the older adult is unable to provide informed

consent and does not have a LAR able to provide informed consent, they will not be able to continue with the study and the in-person assessments and interventions sessions will cease.

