7.3.2 Protection Against Risks

This section describes measures to protect participants against study specific risks, as well as plans for notifying participants of trial results during and after the conclusion of the trial and providing the participants' health providers with the appropriate information from the trial, as needed, concerning individual participants. Study procedures, both assessments and interventions, pose minimal risk to participants. Below we describe potential risks and study procedures to protect against these risks.

The PI ([name]) will be responsible for prompt reporting of new information and other study-related safety information such as study-related or unexpected adverse events and protocol deviations that involve a safety issue to the RSRB, sponsor, federal agencies, and other required entities. Expected, non-study-related adverse events also will be tracked and reported on in the RSRB continuing reviews. The study will be modified to address safety issues or even put on hold if necessary. The PI will review the data periodically to identify any problems and potential risks.

- In order to protect the **confidentiality of subject information**, we will take a number of precautions. These include training research interviewers in confidentiality procedures; entry and storage of data using coded identification labels; maintenance of project computers in secure locations with restricted access by enforced password protection; and use of Health Insurance Portability and Accountability Act (HIPAA) compliant data management software (e.g., REDCap, Box). Back-ups of study files will be made daily to allow for recovery of data due to disk failure. All data, including assessment measures, will be obtained

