10 DATA COLLECTION AND QUALITY ASSURANCE

10.1 Data Collection Forms

Study staff (e.g., CRC, research assistant) will collect and obtain study data directly from the participants (via in-person interviews) as well as from the participant's medical records. The collection, transfer and storage of data will be conducted in compliance with HIPAA and structured to minimize risk of protected health information disclosure. All records related to a participant's research will be stored in locked filing cabinets or on computers protected with passwords. Furthermore, study staff will record data directly into data collection forms that are present in REDCap and all web-based information transmission is encrypted. We also will rely on UR Box to store electronic information, which is HIPAA compliant. The database servers are housed in secure institutional data center facilities at University of Rochester. Additionally, audio recordings of intervention sessions will monitor fidelity and assist with quality control review. These audio recordings will be labeled using de-identified numbers only and will be stored on secure University of Rochester servers and/or the CRC and PI's computers. We will also use an encrypted voice recorder to protect participants' protected health information. Access to these audio recordings will be password protected and audio recordings will be in accordance with local and federal guidelines. The protocol includes a list of the study survey measures (Table 3). During the RN and OT intervention sessions, the RN and OT may decide to skip certain questions/items to focus on issues that are most relevant to each participant. Consequently, study interventionists can, at their discretion, skip or not complete questions in these assessments that they feel are less relevant to the participants they are working with for the study intervention visits. For fields/questions we believe are critical to the study, we will make sure that they require a response in REDCap and cannot be skipped, such as Adverse Event assessments.

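### Does asking about adverse events up to 13 times in the intervention arm but only twice in care-as-usual require a by-arm summary rule in Section 7.2?

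*Combined protocol and SAP*

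**What the plan says.** Section 7.2 sets the AE schedule for the intervention arm: "At each intervention session, study staff will inquire about the occurrence of adverse events and significant adverse events since the last visit". It explains that monitoring is meant to be heaviest while the intervention is heaviest, so that study-related events are found. Section 6.2.3 gives the duty to the interventionists: "The study OT and RN also will monitor for the presence of study-related adverse events at each visit".

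The Schedule of Evaluations in Section 6.1 agrees. Its row reads "Adverse Events | | X | X | | X | X". The columns are screening, baseline, intervention arm, comparator arm, Day 90 and Day 180, so the blank after the second mark is the comparator arm between assessments.

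On recording, Section 10.1 says of critical fields that "we will make sure that they require a response in REDCap and cannot be skipped, such as Adverse Event assessments". On reporting, Section 7.3.2 calls for prompt reporting of study-related or unexpected events and adds: "Expected, non-study-related adverse events also will be tracked and reported on in the RSRB continuing reviews". It does not mention arms.

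Section 9 lists feasibility measures as primary outcomes and home time, quality of life and health care utilisation as secondary outcomes. AEs are in neither list. Section 9.5 limits the analysis to univariate summaries and rules out comparisons across groups.

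**The concern.** The two arms are questioned on very different schedules, and an event asked about sooner is more likely to be remembered. With the same true event rate, a simple AE count by arm would therefore tend to be higher in the intervention arm, mainly for mild self-reported events. That would run against the expectation in Section 7.1 that intervention participants face less risk of events such as falls.

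Section 7.2 has analysis in its title but covers only timing, and no section fixes the look-back for the Day 90 and Day 180 questions. Section 6.2.4 expects that "many participants likely still will be receiving the intervention at the 90 day assessment". If the session wording were carried over to Day 90, an intervention participant might be asked about the past few weeks and a CAU participant about three months.

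At stake would be any descriptive by-arm AE table in the preliminary findings that Section 14 plans to publish, and AE planning for the larger trial. Unlike chance, this bias does not shrink as the sample grows.

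**Working it through.** **1. Contacts after randomisation.** Section 5.1 gives a full dose of 6 OT + 5 RN = 11 sessions, which matches the maximum in the heading of Section 6.2.3. Baseline precedes randomisation (Section 6.2.2) and is not counted.

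- Intervention: 11 + 2 = 13. This is a ceiling, because participants may stop after any visit; five sessions give 5 + 2 = 7.
- CAU: 0 + 2 = 2.

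**2. How far could this move AE counts?** The documents give no recall figure, so the half-life h is an assumption: 60, 90 or 180 days. Assume also equal true risk, a constant event rate over 180 days, and each inquiry covering the time since the previous one. The share of events reported from a window of w days is

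m(w) = (1 − 2^(−w/h)) / ((w/h) ln 2).

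CAU has two 90-day windows, so its capture is m(90) = 0.622, 0.721, 0.845 for the three half-lives. With gaps of g days up to Day 90 and no session after it, the ratio is [m(g) + m(90)] / [2 m(90)]. For g = 14 and h = 60, m(14) = 0.923, and (0.923 + 0.622)/(2 × 0.622) = 1.24.

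| Session pattern | h = 60 | h = 90 | h = 180 |
|---|---|---|---|
| Five weekly sessions, then stop | 1.16 | 1.11 | 1.05 |
| 28-day gaps to Day 90 | 1.19 | 1.12 | 1.06 |
| 14-day gaps to Day 90 | 1.24 | 1.16 | 1.08 |
| 11 even sessions to Day 90 | 1.27 | 1.17 | 1.08 |
| 11 even sessions to day 150 | 1.47 | 1.31 | 1.15 |
| Perfect recall, any pattern | 1.00 | 1.00 | 1.00 |

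The day-150 row does not fit Section 5.1, which front-loads the visits and expects most completers to finish in about 90 days.

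The 90-day first window may also be too long. Section 6.2.4 counts assessments from baseline, but other sections count from discharge, and enrolment may be up to 28 days after discharge. Timed from discharge, the first window could be 90 − 28 = 62 days, and the 14-day row falls to about 1.13, 1.09 and 1.04.

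**3. Against chance.** With 36 and 24 participants and an assumed one event each, the 95% factor for a rate ratio is exp(1.96 × √(1/36 + 1/24)) = exp(1.96 × 0.2635) = 1.68. Every ratio in the table lies inside it.

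**4. Where would the bias enter a planned result?**

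- Primary outcomes (Section 9.4.1): recruitment, retention, fidelity, perceived benefit and data completeness. No AE count is among them.
- Secondary outcomes (Section 9.4.2): home time, quality of life and utilisation. Table 3 collects "Service Utilization: ED, Hospital, Nursing Home Use" at baseline, 3 and 6 months in both arms.
- Falls: Table 3 has "Self-Reported Falls (based on" a CDC survey), again at baseline, 3 and 6 months in both arms.
- Comparisons between arms: none (Section 9.5).
- Review board reports (Section 7.3.2): events are tracked and reported, with no mention of arms.

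No planned result uses an all-source AE count by arm.

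**The case for a change.** The strongest reply is that describing AEs by arm needs no hypothesis test. The investigators intend to publish, readers of a two-arm trial expect AEs by arm, and the source and look-back of a report are easiest to record at data entry and may be hard to recover later. Refining procedures is the purpose of this pilot, and the remedy would cost a paragraph and a form field.

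Part of this stands. The counts are right, the difference in ascertainment is real, and self-reported AEs other than falls and service use have no equivalent schedule in CAU. Anyone who prints AEs by arm should say so, and the larger trial should consider it.

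The rest is weaker.

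- The harm depends on a table the plan never proposes.
- The look-back mismatch depends on extending wording that Section 7.2 applies to intervention sessions only. Asking both arms at Day 90 about the time since baseline is the natural reading, and staff can adopt it without an amendment.
- Required REDCap fields force an answer, which may be none, so they do not in themselves create extra events.
- Restricting by-arm summaries to common sources such as dated chart events and deaths would lean on items that Table 3 does not list in that form. It could also drop session-reported serious events from the by-arm table.

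**Conclusion.** The concern does not call for a change. The unequal schedule is deliberate and sound: interventionists are in the home, risk from the intervention arises there, and CAU has no study visits between assessments. Cutting session inquiries would lose safety information, and adding CAU contacts would alter the comparator.

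The missing summary rule is a gap that an analyst fills sensibly: list all events and all serious events, and if they are shown by arm, note that the intervention arm was asked more often and identify events known only from sessions. Following the plan as written gives no wrong feasibility conclusion and no wrong secondary estimate.

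The contact counts, at most 13 against 2, are firm. The size of any bias is not known. The 1.05 to 1.27 range rests on assumed recall half-lives of 60 to 180 days, equal true risk, a 90-day first window and sessions finished by about Day 90; it would be 1.00 with perfect recall and larger with faster forgetting. The 1.68 chance factor assumes one event per participant. The judgement would change if the plan proposed to compare or interpret AE rates between arms, and it should be revisited if this schedule is carried into the larger trial.
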